10.7	APPENDIX 7: ABBREVIATIONS.....	93
11	REFERENCES.....	95

LIST OF TABLES

Table 1 - Objectives and endpoints	32
Table 2 - Overview of study interventions administered	43
Table 3 - Populations for analyses	69
Table 4 - Efficacy analyses	72
Table 5 - Protocol-required laboratory assessments	85
Table 6 - Highly effective contraceptive methods	91

LIST OF FIGURES

Figure 1 - Graphical study design	19
Figure 2 - Example of selection of skin spots within lesional and non-lesional skin	54
Figure 3 - TEWL assessment and STS in lesional and non-lesional skin of AD patients and in normal skin of HV	55

PROTOCOL AMENDMENT SUMMARY OF CHANGES

DOCUMENT HISTORY

Document	Country/Countries impacted by amendment	Date, version
Amended Clinical Trial Protocol 01	All	28 July 2020, version 1 (electronic 1.0)
Original Clinical Trial Protocol	All	17 March 2020, version 1 (electronic 4.0)

AMENDED PROTOCOL 01 (28 July 2020)

This amended protocol 01 is considered to be substantial based on the criteria set forth in Article 10(a) of Directive 2001/20/EC of the European Parliament and the Council of the European Union.

OVERALL RATIONALE FOR THE AMENDMENT

To further characterize the treatment effect of dupilumab in adolescent and adult patients with moderate to severe atopic dermatitis in reference to match healthy controls, proteomics assessment and transcriptomics assessment from skin tape strips has been added.

These assessments will allow to better assess the mechanism of dupilumab in atopic dermatitis. To have comparable data in lesional skin (LS) and non-lesional skin (non-LS) of AD patients as well as in normal skin of healthy volunteers the number of skin tape strips collected has been set to 20 for each skin area.

A statement concerning the risk-benefit assessment due to COVID-19 has been added.

Protocol amendment summary of changes table

Section # and Name	Description of Change	Brief Rationale
Throughout the document	Inconsistencies and clarification were added to increase clarity of the protocol	Correct inconsistencies
1.1 Synopsis, Secondary endpoints	Additional secondary endpoints for TEWL assessment for lesional, non-lesional and normal skin added	Number of STS assessments in lesional skin increased from 10 to 20, therefore more TEWL assessments are to be conducted. Endpoint assessment in lesional, non-lesional and normal skin has been aligned.
1.1 Synopsis, Tertiary objectives and endpoints	“Proteomics in STS” added	Proteomics will provide additional mechanistic insight in treatment-related effect
1.1 Synopsis, Tertiary objectives and endpoints	“Transcriptomics in STS” added	Transcriptomics will provide additional mechanistic insight in treatment-related effect

Section # and Name	Description of Change	Brief Rationale
1.3 Schedule of activities / AD patients	Line added with proteomics assessment schedule	Implementation of specimen sampling for proteomics
1.3 Schedule of activities / AD patients	Line added with transcriptomics assessment schedule	Implementation of specimen sampling for transcriptomics
1.3 Schedule of activities / AD patients	Footnotes and annotations were added and modified	Increase in clarity and precision
1.4 Schedule of activities / Healthy volunteers	Line added with proteomics assessment schedule	Implementation of specimen sampling for proteomics
1.4 Schedule of activities / Healthy volunteers	Line added with transcriptomics assessment schedule	Implementation of specimen sampling for proteomics
1.4 Schedule of activities / Healthy volunteers	Footnotes and annotations were added and modified	Increase in clarity and precision
Multiple locations in protocol	Proteomics and transcriptomics were added, whenever applicable	Adding proteomics and transcriptomics requires adaptation of multiple sections
2.1 Study rationale	Text added for rationale of the study	Proteins and gene expression changes in AD patients as reason for amendment
2.2 Background	Reference to methods for proteomics and transcriptomics methods	Explanation of methods used
2.3.2 Benefit/risk related to COVID-19	Benefit/risk assessment due to COVID-19 pandemic	Specific section concerning COVID-19 added
3 Objectives and endpoints	Adapted objectives and endpoints due to more STS and TEWL timepoints and due to transcriptomics/proteomics assessment	Number of STS increased, proteomics and transcriptomics added
5.1 Inclusion criteria	For several inclusion criteria the specification has been added for which population this would be applicable. The criteria remain unchanged.	Clarity and precision
5.4 Screen failures	Re-screening of participants is allowed once	To reduce risk of not including participants with temporary reasons for ineligibility
6.1 Study interventions administered	A monitoring period of at least 30 minutes after study drug administration added. Self-injection training modified.	Monitoring period for adverse symptoms specified. Self-injection training modified for more flexibility at the study site.

Section # and Name	Description of Change	Brief Rationale
6.2.1 Storage and handling of IMP	AD patients to inform study site in case of issues with storing IMP	Tracking of adequate storage of IMP provided to patients for self-administration
8 Study assessments and procedures	Monitoring of COVID-19 situation and implementation of alternative methods for patient follow-up described	COVID-19 specific text to describe mechanisms by which the sponsor will react to the pandemic or other public health emergencies
8.2.2 Standardized photographs	Separate ICF for photographs mentioned	Study participants will need to separately consent to publication of photos taken during the study
8.2.3 Questionnaires	Sentence added that patients will bring diary to the site at each visit for review	Clarity and precision
8.9.2 Proteomics	Description of proteomics assessment	Proteomics is an additional study objective
8.9.3 Transcriptomics	Description of transcriptomics assessment	Transcriptomics is an additional study objective
8.9.4 Optional samples for biomarker research	Section has been re-numbered	Due to inclusion of new sections for proteomics and transcriptomics
9.4.7.1 Description of efficacy variables	Biostatistical analysis of additional endpoints	To address additional TEWL and STS endpoints. To address addition of proteomics and lipidomics analysis
9.4.8.1.1 Definitions	Grading of adverse events by NCI CTCAE criteria had been deleted	Grading of non-serious adverse events will be in three categories (mild, moderate, severe) and not in five (mild, moderate, severe, life-threatening, death). The latter two would be documented as serious adverse events
10.1.3 Informed consent process	Separate ICF for agreement to publication of photos taken during the study added	Consistency and clarity to Section 8.2.2

1 PROTOCOL SUMMARY

1.1 SYNOPSIS

Protocol title: Open label exploratory study to evaluate the effect of dupilumab on skin barrier function in patients with moderate to severe atopic dermatitis

Short title: Dupilumab skin BARRIER function and Lipidomics Study in Atopic Dermatitis - BALISTAD

Rationale:

To assess the effect of dupilumab on skin barrier function measured as transepidermal water loss (TEWL) and on skin lipidomics in conjunction with skin tape stripping (STS) in atopic dermatitis (AD) patients.

Objectives and endpoints

Objectives	Endpoints
Primary 
Evaluate changes in skin barrier function with transepidermal water loss (TEWL) assessed after skin tape stripping (STS) in pre-defined lesional skin in patients with moderate to severe atopic dermatitis (AD) treated with dupilumab.	
Percent change from baseline in TEWL after 5 STS assessed on lesional skin at Week16 in AD patients.
Secondary 
Evaluate changes in skin barrier function with TEWL assessed after STS in pre-defined lesional and non-lesional skin in patients with moderate to severe AD treated with dupilumab in reference to normal skin of healthy volunteers.	
Change (percent and absolute) from baseline in TEWL after 20 STS assessed on lesional skin at Week16 in AD patients.Change (percent and absolute) from baseline in TEWL after 20 STS assessed on non-lesional skin at Week16 in AD patients.Change (percent and absolute) from baseline in TEWL after 20 STS assessed on normal skin at Week16 in healthy volunteers.Change (percent and absolute) from baseline in TEWL after 15 STS assessed on lesional skin at Week16 in AD patients.Change (percent and absolute) from baseline in TEWL after 15 STS assessed on non-lesional skin at Week16 in AD patients.Change (percent and absolute) from baseline in TEWL after 15 STS assessed on normal skin at Week16 in healthy volunteers.Change (percent and absolute) from baseline in TEWL after 10 STS assessed on lesional skin at Week16 in AD patients.

Objectives	Endpoints
	
 • Change (percent and absolute) from baseline in TEWL after 10 STS assessed on non-lesional skin at Week16 in AD patients. • Change (percent and absolute) from baseline in TEWL after 10 STS assessed on normal skin at Week16 in healthy volunteers. • Absolute change from baseline in TEWL after 5 STS assessed on lesional skin at Week16 in AD patients. • Change (percent and absolute) from baseline in TEWL after 5 STS assessed on non-lesional skin at Week16 in AD patients. • Change (percent and absolute) from baseline in TEWL after 5 STS assessed on normal skin at Week16 in healthy volunteers.

 • Evaluate time course of skin barrier function with TEWL assessed before and after STS in pre-defined lesional and non-lesional skin in patients with moderate to severe AD treated with dupilumab in reference to normal skin of healthy volunteers. 	
 • Change (percent and absolute) from baseline in TEWL before STS on lesional skin in AD patients over time. • Change (percent and absolute) from baseline in TEWL before STS on non-lesional skin in AD patients over time. • Change (percent and absolute) from baseline in TEWL before STS on normal skin in healthy volunteers over time. • Change (percent and absolute) in TEWL area under the curve (TEWL AUC: a composite measure before and after 5, 10,15 and 20 STS) for skin barrier function in lesional skin in AD patients over time. • Change (percent and absolute) in TEWL AUC (a composite measure before and after 5, 10, 15, and 20 STS) for skin barrier function in non-lesional skin in AD patients over time. • Change (percent and absolute) in TEWL AUC (a composite measure before and after 5, 10, 15, and 20 STS) for skin barrier function in normal skin in healthy volunteers over time. • Change (percent and absolute) from baseline in TEWL after STS assessed on lesional skin in AD patients over time. • Change (percent and absolute) from baseline in TEWL after STS assessed on non-lesional skin in AD patients over time. • Change (percent and absolute) from baseline in TEWL after STS assessed on normal skin in healthy volunteers over time.

Objectives	Endpoints

Tertiary/exploratory
 
 Evaluate dupilumab treatment effect on skin lipidomics using STS samples in both pre-defined lesional and non-lesional skin in patients with moderate to severe AD in reference to normal skin of healthy volunteers. 	
 Changes (percent and absolute) in lipidomics parameters in lesional and non-lesional skin including the ratio of highly hydrophobic ω-esterified fatty acid sphingosine ceramides (EOS CER) and non-hydroxy fatty acid sphingosine ceramides (NS CER), and filaggrin (FLG) breakdown products of urocanic acid (UCA) and pyroglutamic acid (PCA) concentrations at Week 8 and Week 16, respectively. Global characterization of protein-bound ceramides over time.

 Evaluate dupilumab treatment effect on skin proteomics using STS samples in both predefined lesional and non-lesional skin in patients with moderate-to-severe AD in reference to normal skin of healthy volunteers. 	
 Changes (percent and absolute) in the expression of proteins associated with skin barrier function including keratin intermediate filaments, proteins associated with inflammatory response, and glycolysis and oxidative stress response proteins in STS protein extracts over time.

 Evaluate dupilumab treatment effect on skin transcriptome using STS samples in both predefined lesional and non-lesional skin in patients with moderate-to-severe AD in reference to normal skin of healthy volunteers. 	
 Changes in expression of genes associated with epidermal differentiation, barrier and lipid metabolism, and Type 2 inflammation over time.

 Explore the association of skin barrier function measured by TEWL with disease severity assessed by standard AD severity assessments (Eczema Area and Severity Index (EASI), SCORing Atopic Dermatitis (SCORAD), local lesion severity on target lesion), patient reported outcomes (PRO) (Patient Oriented Eczema Measure (POEM), Dermatology Life Quality Index (DLQI) / Children Dermatology Life Questionnaire Index (CDLQI), peak pruritus Numerical Rating Scale (NRS), and quality of sleep NRS), standardized photos, and the biomarker profiles of lipidomics, proteomics, and transcriptomics assessed in the STS sample. 	
 Change (percent and absolute) from baseline in EASI over time. Change (percent and absolute) from baseline in SCORAD over time. Change (percent and absolute) from baseline in Individual Signs Score (ISS) for target lesion over time. Change (percent and absolute) from baseline in PRO (POEM) over time. Change (percent and absolute) from baseline in PRO of DLQI in patients 18 years of age and older / CDLQI in patients ≥ 12 and < 18 years of age over time. Change (percent and absolute) from baseline in PRO of peak pruritus NRS over time. Change (percent and absolute) from baseline in PRO of quality of sleep NRS over time. Change (percent and absolute) from baseline in photograph outputs (eg, severity score) obtained from skin imaging over time. Correlation between baseline values of TEWL before STS and TEWL AUC in lesional and non-lesional skin of AD patients with the following baseline measures: 
 Local target lesion erythema and edema/papulation; ISS EASI, SCORAD

Objectives	Endpoints
	
- PRO measures (POEM, DLQI, CDLQI, peak pruritus NRS, and quality of sleep NRS)- Lipidomics in STS (ratio of EOS CER to NS CER)- Filaggrin breakdown products of UCA and PCA concentrations in STS- Key components of skin proteomics in STS (expression of proteins associated with skin barrier function)- Key components of gene expression from transcriptomics- Image-derived severity score in targeted lesional skin• Correlation between percent change from baseline in TEWL before STS and TEWL AUC in lesional and non-lesional skin of AD patients at Week 8 and Week 16 with corresponding change from baseline in the following measures:
- Local target lesion erythema and edema/papulation; ISS- EASI, SCORAD- PRO measures (POEM, DLQI, CDLQI, peak pruritus NRS, and quality of sleep NRS)- Lipidomics in STS (ratio of EOS CER to NS CER)- Filaggrin breakdown products of UCA and PCA concentrations in STS- Key components of skin proteomics in STS (expression of proteins associated with skin barrier function)- Key components of gene expression from transcriptomics- Image-derived severity score in targeted lesional skin

Overall design:

- Phase IV.
- Two study sites ([name], Denver, USA; [name], Innovaderm, Montreal, Canada).
- Open-label, exploratory study.
- Approximately 24 patients with moderate to severe AD will be enrolled to achieve 20 evaluable patients.
- Approximately 24 evaluable healthy volunteers matched for age, gender, location of skin area, and study site will serve as a reference comparator for skin barrier function.

This is a 16-week, open label, exploratory study designed to investigate dupilumab's effect on skin barrier function as measured by TEWL before and after skin tape stripping in approximately 10 adolescent and approximately 10 adult patients with moderate to severe AD (not more than 12 of either group). During the first 2 treatment weeks, patients will have 2 on-site visits/week, followed by one on-site visit/week up to Week 4, one on-site visit every two weeks from Week 4 to Week 8, and one on-site visit every 4 weeks up to Week 16 End of Treatment phase visit (EoT) thereafter.

A follow-up visit by phone 4 weeks after the last study assessment at Week 16 will end the study for each participant (End of Study: EoS). The maximum duration of the study per participant will be 24 weeks.

Lesional and non-lesional skin areas for TEWL assessment and STS will be identified on the upper limbs or lower limbs at baseline ("predefined skin area"). TEWL and STS-assessment at pre-defined non-lesional (normal looking) skin area in AD patients should be made about 4 cm from the edge of the lesional area.

Within the predefined lesional skin (LS) and non-lesional skin (non-LS) areas three closely adjacent spots will be identified for subsequent skin barrier function assessment (3 spots on lesional skin, 3 spots on non-lesional skin). These spots must not overlap with each other once skin tapes are applied.

The skin barrier function without and before STS will be assessed using TEWL measurement on each of the three spots within these pre-defined skin areas at each visit.

Repeated TEWL assessment in pre-defined lesional and non-lesional skin areas of AD patients after STS for lipidomics, proteomics and transcriptomics analysis in STS samples will be conducted at baseline (Week 0, Day 1), Week 2 (Day 15), Week 4 (Day 29), Week 8 (Day 57), Week, 12 (Day 85), and at EoT at Week 16 (Day 113).

In order to allow the skin to recover from the STS, the skin barrier function assessment with STS will be performed as follows: STS assessment on baseline (Week 0), Week 8 and Week 16 will be conducted on the first spot within the predefined lesional and non-lesional skin area. STS assessment on Week 2 will be conducted on the second spot. STS assessment on Week 4 and Week 12 will be conducted on the third spot.

TEWL will be measured before and after 5, 10, 15, and 20 STS (5 TEWL assessments per visit) on targeted, predefined lesional, non-lesional skin in AD patients at baseline, Week 2, Week 4, Week 8, Week 12, and Week 16 on the predefined first, second or third spot, respectively.

Skin barrier function in approximately twenty healthy volunteers matched for age, gender, location of targeted lesion area, and study site to the AD cases will be assessed in a similar manner at baseline, twice a week during the first two weeks, once a week during Week 3 to Week 4, every two weeks from Week 4 to Week 8, and every four weeks up to Week 16 thereafter, serving as a reference comparator for skin barrier function.

Within the targeted skin area of healthy volunteers -the predefined skin location for TEWL and STS must be identical to the lesional area of the patient to which a healthy volunteer is matched- three closely adjacent spots without an overlap for the skin tapes will be identified for subsequent skin barrier function assessment.

The skin barrier function without and before STS will be assessed using TEWL measurement on each of the three spots at each visit.

On normal skin in healthy volunteers at each visit at baseline, Week 2, Week 4, Week 8, Week 12, and Week 16, TEWL will be measured before and after 5, 10, 15, and 20 STS on the predefined first, second or third spot respectively for skin barrier function assessment (5 TEWL assessments per visit in normal skin) at the same location as for the lesional skin in the matching AD patient and as described above.

In particular, STS assessment on baseline (Week 0, Day 1), Week 8 (Day 57) and Week 16 (Day 113) will be conducted on the first spot within the location-matched, normal skin. STS assessment on Week 2 (Day 15) will be conducted on the second spot. STS assessment on Week 4 (Day 29) and Week 12 (Day 85) will be conducted on the third spot.

Study drug will be administered on-site by study site staff at baseline, Week 2, 4, 6, 8 and Week 12, after the TEWL assessment has been completed. Study drug will be self-administered at home by AD patients at Week 10 and 14.

Intervention groups and duration:

This is a 16-week, open-label study of dupilumab in moderate to severe AD patients. Age-, gender-, targeted lesion area- and study-site-matched healthy volunteers will be included for a non-treatment, 16-week evaluation period. Total study duration including screening and follow-up phone call will be 24 weeks.

Study intervention(s)

Investigational medicinal product(s)

Dupilumab 200 mg

- Formulation: a 175 mg/mL dupilumab solution in a pre-filled syringe to deliver 200 mg in a 1.14 mL subcutaneous injection.
- Route(s) of administration: subcutaneous injection (SC).

Dupilumab 300 mg

- Formulation: a 150 mg/mL dupilumab solution in a pre-filled syringe to deliver 300 mg in a 2 mL subcutaneous injection.
- Route(s) of administration: subcutaneous injection (SC).
- Dose regimen

- For AD patients aged ≥ 12 to < 18 years the dose regimen will be based on body weight on Day 1. No change in dosing will be made if body weight increases or decreases during the study. Dose allocation will be according to the following table:

Body Weight	Loading Dose on Day 1	Subsequent Doses (Q2W) ^a
less than 60 kg	400 mg (two 200 mg injections)	200 mg
60 kg or more	600 mg (two 300 mg injections)	300 mg

^a Every second week (Q2W)

- AD patients age 18 years and older will receive a SC loading dose of 600 mg on Day 1, followed by 300 mg Q2W SC through Week 14. Drug will be administered by study site staff at baseline, Week, 2, 4, 6, 8 and 12. Drug will be self-administered by AD patients at home at Week 10 and 14.

Post-trial access to study medication

- After the study is completed, patients will not be provided with any further study medication as part of this protocol.

Duration of study period (per participant)

Study participation for each patient and healthy volunteer will be a total of approximately 24 weeks including:

- Screening period: Up to 4 weeks from signed informed consent.
- Open label dupilumab treatment (AD patients) and observation period (healthy volunteers): 16 weeks from baseline on Day 1.
- Follow-up period: 4 weeks after the EOT visit at Week 16.

Statistical considerations: Analyses will be descriptive and explorative.

After all patients and healthy volunteers have completed the Week 16 assessments, the data up to this time will be cleaned, and locked; all endpoints relating to Week 16 will be analyzed and reported at this time.

- **Sample size calculations**
 - Sample size for this exploratory study was based on medical/clinical judgement and is consistent with the sample size from similar studies in the literature (1). No formal sample size calculation was performed. TEWL data collected in similar settings as planned for this study were not available: ie, TEWL values after 5 STS, and pre- and post-dupilumab treatment are unknown.
- **Analysis of primary, secondary and exploratory endpoints:**
 - This is an exploratory study. No formal statistical testing will be conducted.
 - Descriptive statistics will be generated by group, time point and type of skin area (lesional or non-lesional, if applicable) for selected parameters of interest. Raw data

and changes from baseline: ie, absolute and percent changes, for selected parameters will be summarized in descriptive statistics and summary plots.

- Evolution over time of TEWL before STS and TEWL AUC by type of skin area will be analyzed. Matched healthy subjects will provide normal reference values.
- **Safety/other analysis:**
 - The safety evaluation will be conducted on all AD patients who receive at least one dose of dupilumab or had at least one TEWL/STS assessment performed, and on all healthy volunteers, who had at least one TEWL/STS assessment. The analysis will be based on descriptive statistics providing summary statistics for vital signs parameters (including summary of Potentially Clinically Significant Abnormalities (PCSAs)) and reported adverse event.

Data Monitoring Committee: None

[figure not shown]

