- g* Peak pruritus NRS and quality of sleep NRS will be assessed daily from Day-7 to Day -1; daily from Day 1 to Day 29 and then for the 7 days prior to Week 6, Week 8, to Week 12 and to Week 16 by e-diary. Patients will bring the eDiary to the site at each visit. eDiary will be reviewed for any questionnaires omission and dispensed back to patients at each visit.
- h* TEWL to be conducted before STS and then after 5, 10, 15, and 20 STS in pre-defined lesional and non-lesional skin. All skin tape strips will be collected and stored.
- i* At Week 0, 8 and 16 STS will be conducted on the first spot within the predefined skin area. At Week 2 STS will be conducted on the second spot within the predefined skin area. At Week 4 and 12 STS will be conducted on the third spot within the predefined skin area. TEWL will be assessed in lesional and non-lesional skin before STS and after 5, 10, 15, and 20 STS. All skin tape strips will be collected and stored for lipidomics, proteomics, and transcriptomics analyses.
- j* Emollients should NOT be applied from Day -7 to the EoT (Week 16, Day 113) to the targeted, pre-defined skin areas that will be used for TEWL assessment. Participants should not take showers or soaking in a bathtub within 6 hours before TEWL assessment. Compliance must be documented in participant's source data. Emollients for use during the study will be provided by the study site to study participants. Use of emollients should be documented in a diary.
- k* Limited to skin-related physical examination at baseline and EoT visit.
- l* Pre-defined lesional (3 spots) and non-lesional skin areas (3 spots), whereby the assessment spots on non-lesional skin are located about 4 cm apart from the edge of the AD lesion.
- m* TEWL will be measured at each of the three closely adjacent spots within the predefined skin areas at all visits as baseline assessment; if there is STS, subsequent TEWL assessment will only be done at the lesional and no-lesional spot, at which STS is performed.
- n* In case STS assessment is to be conducted at an unscheduled visit or at a premature end of treatment visit the assessment should be conducted at that spot of the skin area, for which the period passed since the last STS assessment is the longest.

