4 STUDY DESIGN

4.1 OVERALL DESIGN

This is a phase IV open-label, exploratory study evaluating the effect of dupilumab on skin barrier function in adolescent and adult patients with moderate to severe AD with a healthy volunteer cohort as a reference comparator in two study sites.

The maximum study duration per participant will be 24 weeks. The study will comprise of:

- Screening Period 1 (Day -28 to -1): Subjects will be evaluated according to inclusion and exclusion criteria.
- Baseline Visit (Day 1): Subjects who remain eligible will be enrolled.
- 16-week treatment period for AD patients and a 16-week observation period for healthy volunteers.
- 4-week safety follow-up period.

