5.1 INCLUSION CRITERIA

Participants are eligible to be included in the study only if all of the following criteria apply:

Age

- I 01. Participant must be between 12 to 65 years of age (inclusive), at the time of signing the informed consent.

Type of participant and disease characteristics

Atopic dermatitis patients and healthy volunteers:

- I 02. Male or female patients.
- I 03. Patients with AD diagnosis according to Hanifin and Rajka criteria at least 1 year before screening. (AD patients only)
- I 04. Investigator Global Assessment (IGA) score of ≥ 3 at screening (on the 0-4 scale). (AD patients only)
- I 05. Patients with moderate to severe atopic dermatitis that are eligible to be treated with dupilumab according to product monograph. (AD patients only)
- I 06. Patients with AD must have active lesions on the upper limbs or lower limbs, with severity for lesion erythema or edema/papulation ≥ 2 at screening on the 0-3 scale of the ISS. (AD patients only)
- I 07. Participants should have a non-lesional (normal looking) skin area 4 cm from the edge of the lesional area. If unable to identify non-lesional skin 4 cm from the lesional area, it is acceptable to identify normal looking skin as close to the lesion as possible. (AD patients only)
- I 08. Willing to refrain from applying any topical medication products on the target assessment areas (including lesional and non-lesional) throughout the study until the EoT visit unless necessary to alleviate intolerable symptoms.

- I 09. Willing to refrain taking showers or soaking in a bathtub with soaps and body washes within 6 hours before TEWL assessments.
- I 10. Willing to NOT apply any moisturizers to the areas of the skin that are targeted assessment areas (lesional and non-lesional) during the entire study from Day -7 to the EoT visit.
- I 11. Willing and able to comply with all clinic visits and study-related procedures.

Healthy volunteers only:

- I 12. Age and gender matched to a selected AD patient by study site. Adolescents aged 12 to 17 years will be matched by post puberty status, and adults aged 18 to 65 years will be matched by age as close as possible within 10 years of age.
- I 13. No current dermatologic or systemic condition that could interfere with the assessments.

Weight

Not applicable.

Sex

- I 14. Male or Female

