5.3 LIFESTYLE CONSIDERATIONS

- Study participants should not take a shower or soaking in a bath within 6 hours before assessment of TEWL.
- Emollients for use during the study will be provided by the study site to study participants.
- Participants should apply Cetaphil, Vanicream, or preferred same emollients not containing additives except at the pre-defined skin assessment areas up to two times daily from Day -7 to the EoT visit.
- Participants should not apply any emollients on or within 5 cm of the pre-defined skin assessment areas during the entire study period from Day-7 until the EoT visit.
- The type, amount (number of fingertip units), and frequency of topical products used during the study will be recorded at home in a medication log/diary.

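### Target skin areas are identified on Day 1 but must be emollient-free from Day -7, so the restriction cannot be reliably followed or verified before the baseline TEWL measurement

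*Protocol*

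**What the plan says.** **When the areas are set.** The Synopsis (Section 1.1, overall design) says: "Lesional and non-lesional skin areas for TEWL assessment and STS will be identified on the upper limbs or lower limbs at baseline". The same sentence introduces the term used for these areas in the rest of the protocol. Section 4.1 dates the visit: "Baseline Visit (Day 1): Subjects who remain eligible will be enrolled". A volunteer's location must be the same as the lesional area of the matched patient, so it depends on that choice.

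**When the restriction starts.** Footnote j of the AD schedule (Section 1.3) says: "Emollients should NOT be applied from Day -7 to the EoT (Week 16, Day 113) to the targeted, pre-defined skin areas". Footnote f of Section 1.4 repeats this for volunteers. Criterion I 10 in Section 5.1 asks only for willingness: "Willing to NOT apply any moisturizers to the areas of the skin that are targeted assessment areas (lesional and non-lesional", again from Day -7. Section 5.3 adds a margin: "Participants should not apply any emollients on or within 5 cm of the pre-defined skin assessment areas during the entire study period". Section 6.5 has the same 5 cm buffer for AD patients.

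**What happens on other skin.** Section 5.3 also says: "Participants should apply Cetaphil, Vanicream, or preferred same emollients not containing additives except at the pre-defined skin assessment areas up to two times daily", starting on Day -7.

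**What is checked at screening.** I 06 requires a limb lesion with "severity for lesion erythema or edema/papulation ≥ 2 at screening on the 0-3 scale of the ISS". I 07 requires normal-looking skin near the lesional area. The AD schedule also lists an emollient and washing compliance check at screening, at baseline and at each on-site visit to Week 16.

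**The concern.** A participant can keep emollient off an area, and 5 cm around it, only if the area is known. If it is chosen on Day 1, someone who follows Section 5.3 from Day -7 may treat the very skin that is later selected. Before Week 16 the area has been known for months, so the restriction can be followed. Skin preparation may then differ between the two measurements that make up the primary endpoint.

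The SAP (Section 1.2) compares Week 16 TEWL with Day 1 TEWL at the same number of strips, so Day 1 is the denominator of the primary percent change. It is also the reference for the change-from-baseline TEWL secondary endpoints. Section 6.3 confirms that patients have no treatment control group, so a preparation difference would enter the estimate directly. Volunteers supply reference values; the plan does not use them to adjust the within-patient change. Section 8.2.1.1 presents moisturizer standardisation from Day -7 as a means of controlling the TEWL reading, so the protocol itself regards this as relevant.

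**Working it through.** The plan gives no figure on this point, so the main check is one of timing. (The only computable design number, 20/(1 - 0.15) = 23.5, rounded up to 24 patients, reproduces Section 9.2 and does not bear on the issue.)

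**Step 1: set the sections side by side.**

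| Event | Day | Source |
|---|---|---|
| Screening visit | -28 to -1 | Protocol 1.3, 4.1 |
| Emollient restriction on target areas begins | -7 | Protocol 1.3 (j), 1.4 (f), 5.1 (I 10), 5.3, 6.5 |
| Emollient up to twice daily on other skin begins | -7 | Protocol 5.3 |
| Target areas identified | 1 | Protocol 1.1 |
| First scheduled photographs of target areas | 1 | Protocol 1.3, 1.4, 8.2.2 |
| Restriction ends | 113 | Protocol 1.3 (j), 1.4 (f) |

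As written, the restriction begins a week before the areas it applies to are identified.

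**Step 2: look for an earlier designation.** I 06 needs a qualifying limb lesion but does not make it the target. I 07 needs suitable non-lesional skin but does not mark it. E 02 and E 03 (Section 5.2) refer to the assessment area as if it were known. The ISS and the compliance check are scheduled at screening. These items presuppose an area; none requires one to be fixed before Day 1.

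**Step 3: ask whether a breach would be detected.** The medication log (Sections 5.3 and 8) records type, amount and frequency of topical products; body site is not listed. The compliance check has no designated area to refer to before Day 1. Someone who applied emollient under Section 5.3 before an area existed may register no deviation.

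**Step 4: illustrate the consequence.** Let *f* be the factor by which earlier emollient multiplies Day 1 TEWL after five strips, with Week 16 unaffected. Then

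observed % change = 100 × ((1 + true change)/*f* - 1).

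Both *f* and the true change are assumptions; the documents give neither.

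| True change | *f* = 0.8 | *f* = 0.9 | *f* = 1.1 | *f* = 1.2 |
|---|---|---|---|---|
| -40% | -25.0% | -33.3% | -45.5% | -50.0% |
| -30% | -12.5% | -22.2% | -36.4% | -41.7% |
| 0% | +25.0% | +11.1% | -9.1% | -16.7% |

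Example: 0.60/0.90 - 1 = -33.3%. If only half the patients were affected and the true change were -30%, the observed mean would be 0.5 × (-12.5) + 0.5 × (-30) = -21.3% at *f* = 0.8, and 0.5 × (-41.7) + 0.5 × (-30) = -35.8% at *f* = 1.2.

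**The case against.** The strongest reply is that the Synopsis sentence is loosely worded and that the protocol as a whole implies provisional selection at screening with final placement on Day 1. I 07, E 02, E 03, the screening ISS and the screening compliance check all read more naturally if a lesion has already been picked. A careful participant could leave every candidate limb site untreated, since twice daily is a ceiling. The detailed TEWL procedure is in the study reference manual (Section 8.2.1.2), which is not available here and may settle the matter. This stands as far as it goes: a reader might infer that the areas are chosen only on Day 1 and that the restriction is impossible to follow, and the documents do not support that. They show that earlier designation is not required.

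Safeguards also exist. Emollient use goes in a diary and compliance in source data. Section 9.2 ties evaluability to the absence of major or critical deviations related to TEWL measurement. SAP Section 1.2 removes from the mITT population anyone with a major deviation affecting efficacy data, and the primary endpoint is also run on the ITT population. If emollient on the area were classed as a major deviation, much of a sensitivity analysis would already be in place. But the rule does not name emollients, the classification is left to the study team, and Step 3 shows why a breach might not be seen.

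The screening window, "Screening Period 1 (Day -28 to -1", nominally allows 6 of 28 days (Day -6 to Day -1) after the restriction starts. Little weight belongs here: the daily itch and sleep diary from Day -7 and the one-week topical washout imply that AD patients are usually seen by then. Being seen does not mean that an area has been chosen.

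Finally, the primary reading follows five strips, which remove the uppermost layers, so an emollient effect on it may be smaller than on undisturbed skin. That is possible; the documents are silent.

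**Conclusion.** The conflict is real. The Synopsis places identification on Day 1, five other sections start the restriction on Day -7, and no section of the protocol or SAP requires the area to be designated in between. The restriction therefore cannot be reliably followed or verified in the week before baseline, and Day 1 TEWL may come from recently treated skin while Week 16 TEWL does not.

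A reader might also infer that the primary result is biased, or biased against the drug. Neither follows. How many participants treated the chosen area is unknown, and the documents give no emollient effect on TEWL, in size or direction. The table above shows what assumed shifts of 10% and 20% would do and is not an estimate. It does show that either sign would matter: one dilutes a true fall, and the other could produce an apparent fall of 9.1% to 16.7% with no true change.

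The study is exploratory and no sample size or alpha figure is affected. The change is still worth making, because it reconciles rules the protocol already states and protects the denominator of its primary endpoint.

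**What to change.** 1. Change the Synopsis so that candidate lesional and non-lesional areas are designated and marked, or mapped, at the screening visit, no later than Day -7, and confirmed on Day 1. Align Sections 1.3, 1.4, 5.1, 5.3 and 6.5 with this wording.
2. Set the matched volunteer's location by Day -7 where the patient's area is already known.
3. Record on Day 1 whether each area was emollient-free for the preceding seven days. For participants already past Day 1, use the diary and source records where they allow it.
4. Add to the SAP a sensitivity analysis of the primary endpoint that excludes participants whose area was not emollient-free for those seven days.

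The cost is wording, marking or mapping at an existing visit, one recorded item and one further run of a planned analysis. Screening can fall up to four weeks before Day 1, so a map may serve better than a skin mark. No additional photographs are needed. The downside is small: if the chosen lesion becomes unsuitable by Day 1, a new area needs a short delay.
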